11.3. Data imputation

In the imputation of missing or partial dates, if the imputed date is after min (death date, cutoff date), min (death date, cutoff date) will be used as the imputed date.

If an Adverse Event start date is partially or completely missing, then the following rules will be used for the imputation:

- If the start day is missing then the first day of the month will be used.
- If the start day and month are missing then January 01 will be used.
- If the start date is completely missing then the date of first dose will be used.
- If the end date is complete and the imputed start date is after the end date, then the start date will be imputed as the end date.

If an Adverse Event stop date is missing the date will be imputed as follows:

- If month and year are present, then impute as the last day of that month
- If only the year is present, impute as December 31 of that year
- If the stop date is entirely missing, assume the event is ongoing

The imputation rules for CM are the same as the rules for AE.

Completely or partially missing TA dates will not be imputed.

- In case date of last TA is missing and there are no previous TA dates, then the date of first study drug admin will be used
- In case date of last Ta is missing and there are previous TA dates, then the previous TA date will be used for censoring

If in the eCRF the last tumour assessment of a patient, has been entered as an unscheduled assessment, for analysis purpose it will be associated to End of Study assessment.

Other missing values will not be imputed since for every analysis an observed-cases approach will be applied.

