9.3.5 Data Imputations

Missing values will not be imputed since for every analysis an observed-cases approach will be applied.

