12.1. Efficacy analysis

The following parameters will be summarized by cohort and overall (if appropriate) on the Efficacy population:

- Best Overall Response
- Disease Control Rate
- Objective Response Rate
- Duration of response (DoR)
- Progression Free survival (PFS);
- Overall Survival (OS).

ORR locally assessed is the primary endpoint of the Cohort Expansion Phase. All efficacy

endpoints related to tumour assessment will be evaluated considering both local (secondary endpoints) and central (exploratory endpoints) radiology assessments.

Best Overall Response (BOR) is derived as follows:

- If a subject has at least one overall response of CR, then BOR is CR;
- If a subject doesn't have any overall response of CR but has at least one overall response of PR, then BOR is PR;
- If a subject doesn't have any overall response of CR or PR but has at least one overall response of SD (or Non-CR / Non-PD) at least six weeks after the first intake of MEN1611, then BOR is SD (or Non CR / Non PD);
- If a subject doesn't have any overall response of CR, PR, SD (or Non-CR / Non-PD) after at least 6 weeks from the first intake of MEN1611, but has at least one overall response of PD, then BOR is PD;
- In all other cases, BOR is NE.

Objective Response Rate (ORR) is calculated as the sum of BOR rates of complete response (CR), partial response (PR).

Disease Control Rate (DCR) is calculated as the sum of BOR rates of complete response (CR), partial response (PR) and stable disease (SD).

Overall Survival (OS) is calculated as:

- In case of all-cause death:
OS = date of death - date of first study treatment administration + 1;
- In case of censored information not for drop-out:
OS = date of end of observation period (i.e. maximum between end of study and last follow up date) - date of first study treatment administration + 1;
- In case of censored information for drop-out:
OS = last available date in eCRF - date of first study treatment administration + 1.

Progression-free Survival (PFS) is calculated as:

- In case of death/disease progression:
PFS = date of death or date of first disease progression - date of first study treatment administration + 1
For subjects who experienced both death and progression disease, the date referred to the event that came first is considered.
- In case of censored information due to responding subjects or lost to follow-up:
PFS = date of censoring - date of first study treatment administration + 1

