Detailed censoring rules are as follows:

Circumstances		Options for end-date (progression or censoring)	Outcome
1	Documented Progression	(i) Date of documented progression	Progressed
2	Death without documented progression	(i) Date of death	Progressed
3	Documented progression or death after exactly one missing assessment	(i) Date of progression or death	Progressed
4	Documented progression or death after two or more missing assessments	(i) Date of last adequate assessment ^a	Censored
5	No documented progression and no death (with at least one post baseline assessment)	(i) Date of last adequate assessment	Censored
6	Treatment discontinuation Reason ' Disease progression/clinical progression/progression ' without radiological assessment.	(i) Ignore clinical progression and follow situations above	As per above circumstances
7	No baseline tumor assessment	Date of first study treatment administration	Censored
8	No post baseline assessment and no death	Date of first study treatment administration	Censored
9	Subject lost to follow-up (or withdrew consent) before documented progression or death	(i) Date of last adequate assessment	Censored

^aAfter the last adequate tumor assessment. Date of next scheduled assessment- as specified in the protocol

Duration of Response (DR) is calculated as:

- In case of disease progression:
DR = date of disease progression – date of first occurrence of a BOR of PR, CR or SD + 1
- In case of censored information:
DR = date of last tumor assessment – date of first occurrence of a BOR of PR, CR or SD + 1

Note: subjects with only one assessment post baseline with response equal to PD won't be counted for the DR calculation

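### SAP 11.3 censors at the previous scan when the last scan date is missing, with no exception when that last scan showed progression

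*SAP*

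**What the plan says.** **Scan dates.** SAP 11.3 states "Completely or partially missing TA dates will not be imputed". If the date of the last tumour assessment is missing and earlier dates exist, "In case date of last Ta is missing and there are previous TA dates, then the previous TA date will be used for censoring". If "there are no previous TA dates, then the date of first study drug admin will be used"; this bullet does not say whether the patient then counts as an event or as censored. Neither bullet mentions the result of the undated scan.

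**Progression.** Row 1 of the censoring table in SAP 12.1 classes documented progression as an event, at the "Date of documented progression". No row covers a progression whose date is missing or partial. For PFS, "For subjects who experienced both death and progression disease, the date referred to the event that came first is considered".

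**Death dates.** SAP 11.3 uses the death date only as a known cap on other imputed dates: "if the imputed date is after min (death date, cutoff date), min (death date, cutoff date) will be used as the imputed date". It has no rule for an incomplete death date, which leaves the catch-all: "Other missing values will not be imputed since for every analysis an observed-cases approach will be applied". Protocol 9.3.5 takes the same general position: "Missing values will not be imputed since for every analysis an observed-cases approach will be applied".

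**Contrast.** The same SAP section gives imputation rules for partial adverse-event and concomitant-medication dates. SAP 5.4.2 refers to an Attachment A as the complete list of censoring rules; it is not in the text available for this review.

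**The concern.** Tumour assessment continues until objective progression (SAP 5.4.2), and progression ends study treatment (Protocol 8.2.3.2). The last scan is therefore often the one that shows PD, so a rule about undated last scans falls largely on events. A programmer who follows 11.3 word for word would censor a patient who is known to have progressed, while row 1 of the table calls that patient progressed.

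PFS and DoR are at stake. For PFS, a later death can still provide an event. For DoR it cannot, because SAP 5.4.2 censors responders who die without a recorded relapse. With at most 40 evaluable patients and no control arm, the Kaplan-Meier estimates are what a reader will compare with outside data, so a few recoded events can show.

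A related gap concerns OS. Survival status may be collected by telephone every 12 weeks (Protocol 8.5.1), where a death known only to the month is plausible, and the SAP does not say what happens to it.

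**Working it through.** The documents give no figure for this point, so there is nothing to reproduce. The check has a reading step and an illustrative calculation.

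**1. Following one patient through the text.** Scans at weeks 8 and 16 show stable disease; the week-24 scan shows PD but its date is incomplete. Under 11.3 the week-24 date is not imputed, and the previous date (week 16) is used for censoring. Row 1 of 12.1 would make the patient an event but needs a date that 11.3 does not supply. The best overall response is derived without the PD date. The result is a known progression analysed as censored at week 16.

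**2. Effect on the Kaplan-Meier curve.** Suppose *n* patients are at risk at a scan and *d* progress. The survival factor is (n − d)/n. Recoding one progression as censored one scan earlier changes it to (n − d)/(n − 1), which is at least as large. With scans on a common schedule, the curve moves up or stays.

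**3. Inputs for the size.**
- *n* = 40 evaluable patients (Protocol synopsis, Study Duration).
- Scan interval 2 × 28 = 56 days (SAP 5.4.2), or 56/30.4375 = 1.84 months.
- Median PFS 3.7 months (cetuximab monotherapy, wild-type KRAS), 88 days, and 4.0 months or about 122 days (two cetuximab rechallenge studies), all cited in Protocol 6.2.
- Assumed, not in the documents: exponential times; PD in every patient, read at the next scan; no other censoring; 1, 2 or 4 of 40 progressions with an incomplete date (2.5%, 5%, 10%).

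**4. Hand check of the event rate, 88-day median.** Mean time to the PD scan = 56/(1 − 0.5^(56/88)) = 56/0.357 = 157 days, so total time is 40 × 157 = 6,280 days. With *k* recoded, the rate ratio is [(40 − k)/40] / [(6,280 − 56k)/6,280]: 0.984, 0.967 and 0.933 for k = 1, 2, 4. The event rate falls by about 2%, 3% and 7%; simulation gives the same.

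**5. Simulated mean Kaplan-Meier median PFS.**

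| Input median | Affected of 40 | Full dates | SAP 11.3 read literally |
|---|---|---|---|
| 3.7 months | 1 | 4.52 months | 4.65 months |
| 3.7 months | 2 | 4.55 months | 4.82 months |
| 3.7 months | 4 | 4.53 months | 5.05 months |
| 88 days | about 1 / 2 / 4 | about 115 days | 117 / 120 / 124 days |
| 122 days | about 1 / 2 / 4 | about 147 days | 151 / 155 / 163 days |

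With the 3.7-month input, 6-month PFS rises by 0.8, 1.8 and 3.6 percentage points. These are averages. On a 56-day grid the median of a single trial either stays or jumps by whole scan intervals, so a mean shift of 0.13 month corresponds to roughly 0.13/1.84 = 7% of trials moving one interval, and 0.52 month to roughly 28%.

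**6. OS, secondary point.** Inputs: median 262 days (rechallenge study in Protocol 6.2); assumed administrative censoring between 180 and 720 days; last contact 0 to 84 days before death. Of about 27 deaths, 0.7, 1.4 and 2.7 on average have an incomplete date. Mean median OS is about 265 days with full dates; 271, 274 and 282 days if those deaths are excluded; 274, 281 and 295 days if they are censored at last contact.

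**7. With the event kept.** Dating a partial PD to the first of the month keeps mean median PFS within about 1.3 days of the full-date value. Dating a partial death to mid-month keeps median OS within 0.1 day.

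**The case against.** The strongest reply is that the 11.3 bullet only supplies a date for patients already censored under the table (rows 5 and 9), and that row 1 still governs documented progression. That reading is possible. It does not help an undated PD, because row 1 needs a date and 11.3 forbids imputing one.

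The trigger should also be rare. The protocol plans 100% source data verification (10.4.1), electronic checks with queries (10.2), upload of every image (8.5.1, 10.1.5) and a data review meeting before lock (9.4). This stands and limits the size, but it does not correct the rule. It is also fair that the bullet says missing; its reach to partial dates is inferred from the line above it.

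Some stronger readings are not supported:
- *A known death with a partial date drops out of OS.* SAP 11.3 names no death-date rule. SAP 12.1 also has a branch that censors at the last available date. Exclusion is one of two readings.
- *PFS and OS can only be biased upward.* This holds on average, not always. With deaths at months 1 to 5 the median is 3; excluding the month-5 death lowers it to 2 (2.5 if midpoints are averaged).
- *An undated PD is always lost to PFS.* A later dated death can count as the event, unless row 4 (two or more missing assessments) censors it.
- *A best response of PD with a censored PFS is peculiar to this rule.* Row 4 already allows it.

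**Conclusion.** The point holds for scan dates. As written, SAP 11.3 can censor a known progression and conflicts with row 1 of the table in 12.1. On average this lengthens PFS and DoR: about 0.1 month in median PFS with one of 40 progressions affected, and about 0.5 month with four. These sizes rest on an assumed number of incomplete dates, which the documents do not give and which is probably small, and on the simplifications in the working. They also ignore any PFS event recovered through a later death.

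For death dates the finding is an unspecified rule, not a stated exclusion; both available readings lengthen OS on average.

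The consequence is limited. PFS, DoR and OS are secondary and descriptive, with no formal test. ORR, the primary endpoint of Step 2, is not affected, because CR and PR enter best overall response without a date; only the six-week check for stable disease, and so disease control rate, uses one. Attachment A may contain a relevant rule; if so, it must be reconciled with 11.3. The correction is still worth making before database lock because it costs almost nothing.

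**What to change.** In SAP 11.3 and the table in 12.1:

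1. Limit the previous-assessment rule to last assessments that do not show PD, and say whether missing includes partial dates. State whether the first-dose bullet yields a censored patient, and exclude PD from it too.
2. For a PD with an incomplete date, keep the event for PFS and DoR. Take the date from the uploaded image. Failing that, use a prespecified imputed date (for example, the earliest that the partial date allows), no earlier than the day after the previous assessment and no later than the earlier of death and cut-off.
3. For a known death with a partial date, keep the event, with a conventional imputed date (for example, mid-month) bounded by the date last known alive and the cut-off.
4. Align Attachment A with these rules, record the departure from Protocol 9.3.5 in SAP 3.1, and report how many dates were imputed.

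The cost is a few sentences and minor programming. The images are already collected, so most scan dates should be recoverable without imputation. The choice among imputation conventions matters little; keeping the event is what matters.

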11.4. Patient disposition and Baseline tables

Patient disposition

The number of patients screened, rescreened, the number of screening failures, and the number of patients in each population (DLT, Safety, Efficacy and PK) will be presented by cohort and overall. In these tables, the percentages will be calculated using the total number of patients in the Safety population in the respective cohort as the denominator (when appropriate).

The number and percentage of patients who discontinued the treatment and who withdrawn the study, with the respective reasons, will be summarized by cohort and overall in two different tables.

Demographic and baseline data

The following demographic, disease and baseline characteristics will be summarized by cohort and overall using descriptive statistics (as described in Section 5.2.1) computed on the Safety population:

- Age (years)
- Ethnicity
- Gender
- Weight (Kg)
- Height (cm)
- BSA (m²). Mosteller formula will be used for BSA calculation:
$$\text{BSA (m}^2\text{)} = \text{sqrt}\{(\text{height (cm)} \times \text{weight (kg)})/3600\}$$
- ECOG PS at baseline
- Tumor location

- Grade
- Stage at diagnosis
- Presence of metastases
- Number of previous cancer treatments
- Number of previous metastatic cancer treatments
- Mutational results (K-RAS, N-RAS, BRAF, PIK3CA)

Medical History and Procedure History

Medical history will be coded using the Medical Dictionary for Regulatory Activities (MedDRA). The number of patients with at least one recorded medical history and current medical condition will be presented using frequency counts and percentages by System Organ Class (SOC) and Preferred Term (PT).

Analogous table will be produced also for Procedure History.

The safety population will be used as analysis population for these tables.

Note: Medical History are those conditions which are not ongoing at the date and time of first MEN1611 intake; current medical conditions are the ones ongoing at the date and time of first MEN1611 intake.

Anti-cancer, Prior and/or Concomitant medications and Procedures

Anti-cancer, Prior and/or Concomitant medications and Procedures will be coded using the WHO drug dictionary and summarised by PT and by Anatomical Therapeutic Chemical (ATC) category level.

The safety population will be used as analysis population for these tables.

Note: Prior medications/procedures are those with start and end dates prior to the date and time of first MEN1611 intake, concomitant medications/procedures are those with start and end dates after the date and time of first MEN1611 intake, prior and concomitant medications are those with start date prior to the date and time of first MEN1611 intake and end date after the date and time of first MEN1611 intake or still ongoing.

Prior Radiotherapy

The number of patients with at least one recorded prior radiotherapy, classified by reason for regimen and location of administration, will be presented using frequency counts and percentages.

The safety population will be used as analysis population.

Substance use

The number of smoker/non smoker patients will be presented using frequency counts and

percentages along with duration of smoking and number of cigarettes smoked per day, in a table by cohort.

Virology

A summary table of Virology results obtained at Screening visit with frequencies and percentages, calculated considering the patients who have performed the examination at each visit, by cohort will be provided in the TLFs

11.5. Safety analysis

Safety analysis will be performed on the safety population through descriptive statistics during each study phase. Summary statistics (N (%) and number of events) will report the incidence of the AEs using combinations of the following variables for the descriptive stratification: toxicity grade, dose level, relationship to study treatment, System Organ Class and Preferred Term and overall.

Also AEs summary tables will be created by cohort and overall.

Counts and percentages will be reported for the results of ECG, laboratory values, vital signs, physical examination, all classified as Normal/Abnormal Not Clinically Significant/Abnormal Clinically Significant by cohort (dose level) and visit.

11.5.1. Safety assessments

Safety and tolerability endpoints will be derived from the following measurements/evaluations:

- Incidence, intensity, CTCAE v.4.03 grading, seriousness and treatment-causality of TEAEs;
- Frequency of clinically significant abnormalities in:
 - Physical examination and vital signs
 - Safety laboratory tests
 - 12-lead ECG record
 - Urinalysis.

11.5.2. Treatment Exposure and Compliance

Cumulative dose is the sum of doses taken during the course of the study.

For MEN1611:

- cumulative dose (mg) is calculated as the sum of the number of capsules taken at each occasion multiplied by the strength of each capsule (16 mg).
- Treatment duration (days) is calculated as (Last dose date – First dose date + 1)

For Cetuximab:

- cumulative dose (mg) is the sum of volumes (mL) administered at each infusion multiplied by the amount of cetuximab contained in the solution (i.e. 5 mg/mL)
- Treatment duration (days) is calculated as (End date of last cycle – First dose date + 1).

End date of last cycle is the earliest of the following dates: the expected end date of last cycle, date of death, date of last known alive, date of subject withdrawal from the study, or the analysis cut-off date if subject is known to be alive after analysis cut-off date.

Expected end date of last cetuximab cycle is calculated as the Date of Day 1 of last cycle + 27 days.

Number of cycles will be determined based on the drug administrations occurred: if at least one dose of any treatment is administered during a cycle, that cycle will be taken into account.

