
Study Duration
 
The overall study duration will depend on the completion of the dose levels/cohorts, the number of patients to be treated per each dose-cohort and the completion of Step 2 up to a total of 40 evaluable patients for efficacy.
 
All patients pre-screened for the PIK3CA mutation will undergo a maximum 4 weeks Screening Period.
 
Each treatment cycle will last 28 days.
 
Individual study duration will depend on the duration of the study treatment which continues up to disease progression or study discontinuation for other reasons.
 
The End of Study Visit will be performed 4 weeks after the last dose of MEN1611.
 
Survival Follow-up:
 
After the End of Study Visit, all patients evaluable for efficacy will be followed for survival status according to local practice (a visit or a telephone call) every 12 weeks up to the End of Study.
 
End of Study:
 
The study ends with the End of Study Visit of the last patient who discontinues the study treatment.
 
For safety monitoring, all serious adverse events (SAEs) with a suspected causal relationship to the study treatment that occur after the End of Study must be recorded and notified to the Sponsor.
	

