8.4.2 Cetuximab

In both Step 1 and Step 2, cetuximab will be administered IV weekly on Day 1, 8, 15 and 22 of every 28-day cycle according to institutional standards.

[figure not shown]
The initial cetuximab dose is 400 mg/m^2 administered as a 120 minutes infusion on Day 1 of Cycle 1, followed by a weekly 250 mg/m^2 dose administered as a 60-minute IV infusion. Premedication with a H1 receptor antagonist (e.g. d-chlorpheniramine or diphenhydramine) and a corticosteroid is required prior to cetuximab administration (see Section 8.4.8). Management of infusion reactions due to cetuximab are to be managed according to Section 8.4.5.

[figure not shown]
MEN1611 will be given in combination with weekly IV infusion of cetuximab until objective disease progression is documented or another criterion for discontinuation is met. If cetuximab needs to be discontinued due to toxicity, continuation with MEN1611 as monotherapy should be considered and discussed with the Sponsor.

[figure not shown]

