5.1. Study configuration and structure

Overall Study Design and Plan Description

This is an open-label, dose-confirmation and cohort expansion, multicenter, Phase Ib/II study to be conducted in approximately 29 sites in Europe and US.

[figure not shown]
The study will consist of 2 sequential steps:

Step 1 (Confirmation of Dose for Cohort Expansion):

Step 2 (Cohort Expansion Phase):

Treatment regimen

MEN1611

Step 1 (Dose-confirmation Phase): MEN1611 as oral capsules of 16 mg strength will be orally administered BID (approximately 12 hours apart) for a continuous 28-day cycle. The starting dose of MEN1611 will be 48 mg BID for a total daily dose of 96 mg. In case 48 mg BID in combination with cetuximab will represent the toxic dose level for this combination, a lower dose level of 32 mg BID will be tested in cohort 2.

In this Phase, MEN1611 will be administered as below:

- Cohort 1: MEN1611 48 mg (3 × 16 mg) capsules BID over 28-days' cycle.
- Cohort 2: MEN1611 32 mg (2 × 16 mg) capsules BID over 28-days' cycle.

Step 2 (Cohort-expansion Phase): MEN1611 as oral capsules will be orally administered BID for a continuous 28-days' cycle at the RP2D as established in Step 1.

MEN1611 capsules should be taken with a glass of water in fasting condition, i.e. at least 2 hours after a meal and at least 1 hour before the next meal. Patient should take capsules at approximately the same time each day. At Visit 2, Visit 3 and Visit 4 of Cycle 1, and at each following visits, MEN1611 will be administered at site using the new boxes dispensed at each visit.

[figure not shown]
Cetuximab

In both Step 1 and Step 2, Cetuximab (solution for infusion) will be administered IV weekly on Day 1, 8, 15 and 22 of every 28-day cycle according to institutional standards. The initial cetuximab dose is 400 mg/m² administered as a 120-minute infusion on Day 1 of Cycle 1, followed by a weekly 250 mg/m² dose administered as a 60-minute IV infusion. Premedication with a H1 receptor antagonist (e.g. d-chlorpheniramine or diphenhydramine) and a corticosteroid is required prior to cetuximab administration (see Section 8.4.8). Management of infusion reactions due to cetuximab are to be managed according to Section 8.4.5. MEN1611 will be given in combination with weekly IV infusion of cetuximab until objective disease progression is

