documented or another criterion for discontinuation is met. If cetuximab needs to be discontinued due to toxicity, continuation with MEN1611 as monotherapy should be considered and discussed with the Sponsor.

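### SAP 11.5.2 runs cetuximab treatment duration to day 28 of the last cycle whatever the last infusion date, which overstates exposure to a weekly drug by 0 to 21 days

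*SAP*

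**What the plan says.** SAP 11.5.2 defines treatment duration differently for the two drugs. For MEN1611 it is last dose date minus first dose date, plus 1. For cetuximab the end point is the end date of the last cycle: "Expected end date of last cetuximab cycle is calculated as the Date of Day 1 of last cycle + 27 days". The end date used is whichever comes first of that expected date, death, the day the patient was last known to be living, withdrawal from the study, or (for patients known to be alive beyond it) the analysis cut-off.

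The same section then says how cycles are counted: "if at least one dose of any treatment is administered during a cycle, that cycle will be taken into account".

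On the schedule, Protocol 8.4.2 states that "cetuximab will be administered IV weekly on Day 1, 8, 15 and 22 of every 28-day cycle". SAP 5.1 agrees: after the loading dose, treatment is "followed by a weekly 250 mg/m² dose administered as a 60-minute IV infusion". The protocol synopsis sets the cycle length: "Each treatment cycle will last 28 days".

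The drugs can be stopped separately. If cetuximab is discontinued for toxicity, "continuation with MEN1611 as monotherapy should be considered and discussed with the Sponsor" (SAP 5.1; Protocol 8.4.2 has the same provision).

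Extent of exposure is a planned output (Protocol 9.3.4) and is reported in SAP Table 2.1.

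**The concern.** Crediting 28 days from Day 1 of the last cycle would suit a drug given once per cycle. For a weekly drug it gives the same duration to a patient who had one infusion in the last cycle as to a patient who had all four. The two drugs' durations in Table 2.1 would also rest on different conventions, with no reason given.

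The patients affected are those who stop cetuximab partway through a cycle. Safety and tolerability of the combination is a secondary objective, and time on cetuximab is part of how a reader judges whether the combination can be sustained. For these patients the table would show time on cetuximab that includes weeks in which none was due to be acting.

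There is also a wording problem. SAP 11.5.2 speaks of the last cycle in some places and the last cetuximab cycle in another, and counts a cycle when either drug was given. It is not certain that two programmers would pick the same last cycle for a patient who went on to MEN1611 alone.

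**Working it through.** **Inputs.** Cycle length 28 days (protocol synopsis). Infusions on Days 1, 8, 15 and 22 (Protocol 8.4.2). End of last cetuximab cycle = Day 1 + 27 days; duration = end date − first dose date + 1 (SAP 11.5.2). Assumption, not in the documents: each weekly infusion covers 7 days, so coverage ends on the infusion date + 6 days. Infusions are taken to fall on their scheduled days, and no cap applies earlier.

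**The SAP's own figure.** Day 1 + 27 = Day 28, a full 28-day last cycle. This reproduces.

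**Excess within the last cycle.** With the last infusion on day *d*, the SAP ends at Day 28 and weekly coverage ends at Day *d* + 6. Excess = 28 − (*d* + 6). For comparison, under the last-dose rule that the SAP uses for MEN1611, excess = 28 − *d*.

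| Last infusion | Coverage ends | Excess, 7-day coverage | Excess, last-dose rule |
|---|---|---|---|
| Day 1 | Day 7 | 21 days | 27 days |
| Day 8 | Day 14 | 14 days | 20 days |
| Day 15 | Day 21 | 7 days | 13 days |
| Day 22 | Day 28 | 0 days | 6 days |

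**Relative size, largest case (last infusion on Day 1 of cycle *k*).** SAP duration = 28*k*; covered duration = 28(*k* − 1) + 7.

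| *k* | SAP | Covered | Excess |
|---|---|---|---|
| 1 | 28 | 7 | 21 (+300%) |
| 2 | 56 | 35 | 21 (+60%) |
| 3 | 84 | 63 | 21 (+33%) |
| 4 | 112 | 91 | 21 (+23%) |
| 6 | 168 | 147 | 21 (+14%) |

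The absolute excess depends only on which weekly infusion was the last. The percentage falls as the number of cycles rises.

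**Do the caps remove it?** The caps are death, last known alive, study withdrawal and cut-off. Protocol 8.2.3.1 and 8.2.3.2 treat withdrawal from the study and withdrawal from study treatment as separate events, and only the former is a cap. A patient who stops cetuximab and stays on study taking MEN1611 meets none of the caps while alive, on study and before cut-off. For example, Protocol 8.4.5 requires permanent cetuximab discontinuation after a severe infusion-related reaction. A patient for whom that happened at the first infusion, and who continued MEN1611, would be reported with 28 days of cetuximab on the narrower reading of last cycle.

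**Effect of the wording.** Assumed example: last cetuximab infusion on Cycle 2 Day 1, MEN1611 through Cycle 6.

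- Last cycle = last cycle with cetuximab: 28 × 2 = 56 days.
- Last cycle = last cycle with either drug: 28 × 6 = 168 days.
- Covered: 28 + 7 = 35 days.

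On the second reading the excess is 168 − 35 = 133 days, which is 21 + 4 × 28. The two readings differ by a factor of 168/56 = 3.

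**Where the quantity is used.** SAP 11.5.2 defines cumulative dose, treatment duration and number of cycles. No formula in either document divides dose by duration. The response and time-to-event derivations (SAP 12.1), the DLT population (SAP 7.3, based on percentage of dose received in Cycle 1) and the adverse event tables (SAP 11.5.3, patient and event counts) do not use treatment duration.

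**The case against.** The strongest defence is that a cycle-based duration is disclosed and matches the protocol's 28-day treatment unit. It is capped at sensible dates, and it feeds only one descriptive table. Cumulative cetuximab dose is computed from administered volumes and is unaffected. Tolerability is shown directly by the tables of adverse events leading to interruption, withdrawal or dose modification, and individual infusions appear in Listing 5.26. Scheduled scans fall in the 7 days before Day 1 of Cycles 3, 5, 7 and so on, so a patient stopped by a scheduled scan will usually have had the last infusion near Day 22, with an excess near zero. All of this stands, and it limits the importance of the point. It does not make the number right for a patient who stops cetuximab mid-cycle.

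Three stronger readings are tempting, and the documents do not support them.

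- *Dose intensity is understated.* A reader might infer this because dose per unit time would fall if divided by too long a duration. Neither document plans a dose intensity, so no planned result is biased this way. It would matter only if one were later derived from this duration.
- *Patients who stop early for toxicity have the most inflated duration.* In days, the excess does not depend on the reason for stopping or on the cycle. A toxicity stop after the Day 22 infusion has none. Only the percentage is larger in early cycles.
- *MEN1611-only cycles are counted as cetuximab time.* The any-treatment sentence governs the number of cycles, and the sentence giving the expected end date names the last cetuximab cycle. Including MEN1611-only cycles is one reading of loose wording, not a stated rule.

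**Conclusion.** The point holds as a limited defect in one exposure derivation. For a weekly drug, the SAP rule overstates cetuximab duration by 21, 14, 7 or 0 days according to whether the last infusion was on Day 1, 8, 15 or 22. This rests on 7-day coverage per infusion, scheduled infusion days, no earlier cap, and last cycle meaning the last cycle with cetuximab. Against the MEN1611 last-dose convention the figures would be 27, 20, 13 or 6 days.

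The caps do not protect patients who stop cetuximab and continue MEN1611 alone, which the plan expressly allows. How many patients this concerns cannot be judged from the documents, so no average effect can be given. Separately, the definition of last cycle is ambiguous, and the wider reading would add 28 days for each MEN1611-only cycle.

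The consequence is confined to Table 2.1. The primary endpoint and the other efficacy results are untouched. The change is worth making before reporting because it is cheap and removes an ambiguity, not because any main conclusion depends on it.

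**What to change.** In SAP 11.5.2:

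- Define the cetuximab end date as the earliest of (last cetuximab infusion date + 6 days) and the existing caps: death, last known alive, study withdrawal, analysis cut-off.
- Define cetuximab duration as that end date − first cetuximab infusion date + 1.
- Count cycles separately for MEN1611 and cetuximab, using only cycles in which the drug concerned was given. This settles the last-cycle wording.
- State the 7-day coverage convention in a footnote to Table 2.1, so that the difference from the MEN1611 last-dose rule is visible.

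The cost is a SAP wording change and minor reprogramming. The infusion dates should already be available, since Listing 5.26 reports cetuximab intake, so no new data are needed. Reported cetuximab duration becomes shorter for patients who stop mid-cycle, and it will no longer be a whole number of cycles for them.
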